#### **5.1 Preparation of Ad-RTS-hIL-12**

Ad-RTS-hIL-12 will be supplied in single-dose vials. [REDACTED]

[REDACTED]

#### **5.2 Preparation of Veledimex**

Sponsor will provide veledimex capsules to be dispensed by the study site pharmacy to subjects for oral administration. [REDACTED]

### **5.3 Handling and Storage**

Investigational product must be stored in a restricted access area under the storage conditions indicated in the Investigator's Brochure [REDACTED]. All necessary precautions while handling potentially toxic compounds must be strictly followed.

### **5.4 Monitoring of Subject Adherence and Managing Missed Veledimex Doses**

The first veledimex dose will be given in the clinic 3 hours  $\pm$  3 hours before Ad-RTS-hIL-12 injection is expected under careful medical supervision by the clinic staff to ensure that the subject does not have difficulty swallowing the capsules. Thereafter, subjects may be allowed to self-administer the remaining once daily doses as described in [Section 6.2](#). Subjects are to be instructed to take the appropriate number of capsules in the same way for each of the remaining treatment period days. All daily capsules must be taken together on the same day and within a few minutes.

Subjects should NOT make up any missed doses. If any dose is missed, a subject should take the next dose as scheduled on the next day.

Each subject will be carefully monitored for possible local reactions at the injection site and/or hypersensitivity reactions for at least 2 hours following the Ad-RTS-hIL-12 injection. The subject should be instructed to call the clinical site if any such reactions develop or do not resolve within 24 to 48 hours.

Subjects should be instructed to document veledimex dosing compliance in a subject diary, including the time subject took the once daily dose, the time subject ate last meal prior to administration of veledimex, the number of capsules taken, whether subject missed any veledimex doses and the study day and reason for any missed doses. Investigational product container(s) with any remaining capsules should be returned to the study staff on Day 8, so that staff can properly assess dose compliance.

### **5.5 Disposition of Unused Drug**

All unused investigational product should be destroyed at the study site in accordance with standard institutional practice and in accordance with US Occupational Safety and Health Administration procedures, after full accountability has been documented. Any investigational product destruction at study site must be documented and the records maintained in the investigator's study file.

### **5.6 Accountability and Dispensation**

The investigator must maintain accurate records accounting for the receipt and dispensation of investigational product. The investigational materials are to be prescribed only by the investigator or the sub-investigators named on the United States Food and Drug Administration (US FDA) Form 1572, and may only be dispensed by authorized personnel at the institution(s) listed therein. Under no circumstances will the investigator allow the investigational drug(s) to be used for purposes or in patients other than as directed by the protocol.

## 6 TREATMENT PLAN

### 6.1 Ad-RTS-hIL-12 Dosage and Administration Procedures

The 0.5 mL dose of Ad-RTS-hIL-12 [REDACTED] must be injected into the same lesion and should be delivered by multiple injections with a fine needle (no finer than 27 gauge) directly into each quadrant of the lesion. Attention must be paid to adequately infiltrate the circumference of the tumor margins. Should the tumor selected for injection not support the entire Ad-RTS-hIL-12 injection volume (approximately 0.5 cc), another tumor should be injected with the remaining volume to ensure that all subjects receive [REDACTED]

[REDACTED] If another tumor is not available, then the remaining volume should be injected into a draining, pathologic lymph node of the injected tumor if possible. Lesions displaying signs of localized infection should not be injected.

**Note:** In the event that Ad-RTS-hIL-12 injection is not performed, subject will not continue in the study. The reason why injection was not given will be documented and the subject will be withdrawn from the study.

Administration of prophylactic antipyretics is strongly recommended during the first week after Ad-RTS-hIL-12 injection (see [Section 6.9](#) and [Appendix 16.2](#)). See note in [Section 6.2](#) concerning importance of proper hydration during treatment with Ad-RTS-hIL-12 immunotherapy.

### 6.2 Veledimex Dosage and Administration

Veledimex will be supplied by the Sponsor as gelatin capsules for oral administration. Subjects will receive 80 mg of veledimex on days 1 through 7. On day 1, veledimex will be administered in a fasting state 3 hours  $\pm$  3 hours before the tumor biopsy and intratumoral injection of Ad-RTS-hIL-12. On days 2 through 7, subjects will be directed to take the veledimex in a fed state (preferably within 30 minutes following a normal meal), once daily, and at the same time ( $\pm$  1 hour) each day. All daily capsules must be taken together on the same day and within a few minutes. Subjects should NOT make up any missed doses. If any dose is missed, a subject should take the next dose as scheduled on the next day.

**Note:** Subjects should be carefully monitored for possible local reactions and/or hypersensitivity reactions, according to standard practice.

[REDACTED]

Administration of prophylactic antipyretics is strongly recommended during the first week after Ad-RTS-hIL-12 injection (see [Section 6.9](#) and [Appendix 16.2](#)).

### 6.3 Dose Escalation

Not applicable.

#### **6.4 Modification of Dose Schedule**

Subjects will receive only one cycle of Ad-RTS-hIL-12 immunotherapy. If a dose of veledimex (up to 2 doses) is held for related toxicity, the treatment related AEs must have resolved to Grade 2 or less for dosing to resume. The held doses will not be made up; the patient will complete dosing according to the remaining schedule.

If a patient misses a dose, the patient is allowed to resume dosing at the next scheduled dose, but must complete dosing according to the remaining schedule. The missed dose will not be made up.

#### **6.5 Dose-Limiting Toxicity**

Not applicable.

#### **6.6 Maximum Tolerated Dose**

Not applicable.

#### **6.7 Dose Modifications and Dose Delays**

Please refer to [Section 6.4](#).

Subjects who experience drug-related Grade 3 AEs during the first 7 days of oral dosing with veledimex will interrupt/discontinue further dosing at the discretion of the investigator. Subjects who experience drug-related Grade 4 AEs during the first 7 days of oral dosing with veledimex will discontinue therapy. The decision as to whether subjects who experience severe or serious treatment-related adverse events will remain on study will be made by the investigator in conjunction with the Sponsor medical monitor.

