##### Ad-RTS-hIL-12

Ad-RTS-hIL-12 will be supplied by the Sponsor as a sterile suspension for injection. Subjects will receive an intratumoral injection of [REDACTED] a volume of 0.5 mL on day 1, 3 hours  $\pm$  3 hours after administration of veledimex.

The 0.5 mL dose of Ad-RTS-hIL-12 should be injected into the same lesion and should be delivered by multiple injections with a fine needle (no finer than 27-gauge) directly into each quadrant of the lesion. Attention must be paid to adequately infiltrate the circumference of the tumor margins. Should the tumor selected for injection not support the entire Ad-RTS-hIL-12 injection volume (approximately 0.5 cc), another tumor should be injected with the remaining volume to ensure that all subjects receive [REDACTED]. If another tumor is not available, then the remaining volume should be injected into a draining, pathologic lymph node of the injected tumor. Lesions displaying signs of localized infection should not be injected. The lesion chosen for injection will be designated as a non-target lesion.

Each subject will be carefully monitored for possible local reactions at the injection site and/or hypersensitivity reactions for at least 2 hours following the Ad-RTS-hIL-12 injection.

All subjects receiving Ad-RTS-hIL-12 immunotherapy must be adequately hydrated with approximately 2000 ml of oral liquid preferably containing electrolytes every 24 hours for the first 72 hours. Subjects must be instructed to maintain good oral hydration on and between dosing days. Additional details regarding the number and selection of lesions and injection of Ad-RTS-hIL-12 is provided in [Section 6.1](#) of the protocol.

Only one cycle of Ad-RTS-hIL-12 immunotherapy will be given.

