## SCHEDULE OF STUDY PROCEDURES

ACTIVITY	SCREENING	Ad-RTS-hIL-12 IMMUNOTHERAPY CYCLE				INITIAL FOLLOW-UP		LONG-TERM FOLLOW-UP			
	D-28 to D-1	D1	D3	D8	D21 p	W6 u	W12 u	W18 u	W24 u	W36 u	W48 u
Informed Consent	X										
Medical/Cancer History	X										
Physical Exam a	X	X	X	X		X	X				
ECOG performance status	X	X	X	X		X	X				
Height	X										
Weight	X	X				X	X				
Vital Signs b	X	X	X	X		X	X				
Adverse Events	X					X t					
Concomitant Medications c	X					X					
Pregnancy d	X										
Hematology e	X	X	X	X		X	X				
Coagulation f	X			X							
Serum Chemistry g	X			X		X	X				
Urinalysis h	X	X									
Tumor markers (CEA, Ca 15-3)	X					X	X				
TSH, Hepatitis B/C, HIV	X										
ECG i	X										
Oral veledimex j,k		X	X								
Intratumoral Ad-RTS-hIL-12		X l									
Dispensing of veledimex for home administration and diary m		X									
Diary collection m		X	X	X							
Imaging Studies n	X					X q	X r	X r	X r	X r	X r
Tumor biopsy		X s				X					
Research bloods o	X	X	X	X		X	X				

Abbreviations: D, day; W, week; ECOG, Eastern Cooperative Oncology Group

- a. A physical exam is required during screening and at Weeks 6 and 12. Otherwise, a symptom-directed physical exam should be performed where indicated.
- b. Vital signs include blood pressure, pulse, temperature, and respirations. On Days 1 and 3 vital signs will be recorded prior to administration of veledimex. On Day 1, vital signs will also be recorded prior to administration of Ad-RTS-hIL-12. At all indicated time points, blood pressure should be monitored closely, [REDACTED] [REDACTED] Subjects must be instructed to maintain adequate oral hydration while taking veledimex; sites must closely monitor subjects' hydration status. Oral hydration (approximately 2000 mL oral electrolyte solution over 24-hours x 3 days) and administration of prophylactic antipyretics are highly recommended after injection of Ad-RTS-hIL-12.
- c. Concomitant medications should be collected from screening through Week 12. In addition, any new anti-cancer medication started prior to confirmation of radiographic response of PD should be collected.

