- d. Females of childbearing potential will have a serum pregnancy test during screening (within 14 days of dosing) and a urine pregnancy test at Day 1. A serum pregnancy test should be completed on Day 1 if the urine pregnancy test is positive.
- e. The hematology panel includes complete blood count (CBC) and white blood cell (WBC) count, differential white blood cell count, red blood cell (RBC) count, hematocrit, hemoglobin, red blood cell indices (MCV, MCH, MCHC), and platelet count.
- f. The coagulation panel includes activated partial thromboplastin time (aPTT) and the international normalized ratio (INR).
- g. The serum chemistry panel includes aspartate transaminase (AST), alanine transaminase (ALT), lactate dehydrogenase (LDH), alkaline phosphatase (ALP), creatinine, total bilirubin, total protein, albumin, blood urea nitrogen (BUN), glucose, sodium, potassium, chloride, calcium, phosphorus, and bicarbonate.
- h. The urinalysis panel (dipstick) includes appearance, pH, specific gravity, glucose, protein/albumin, blood, ketones, bilirubin, nitrates, and leukocyte esterase. In addition, a microscopic exam for casts, crystals, and cells may be done if clinically indicated.
- i. Standard, 12-lead ECG.
- j. Oral veledimex to be taken daily on Days 1-7. The first dose of veledimex will be given at the clinical site in a fasting state. The remaining 6 doses can be self-administered at the same time as on Day 1 ( $\pm$ 1 hour) by subjects, in the fed state, on Days 2-7. Study sites must verify adherence with veledimex dosing. Subjects should return bottles of veledimex to the clinical site to determine extent of subject adherence to self-administration preferably on Day 8.
- k. Days 2, 4, 5, 6, and 7 are not shown, but veledimex is also to be taken on those days.

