#### 8.3.1.3 Vital Signs, Height and Weight

Vital signs will include blood pressure, pulse rate, temperature, and respiration rate. Subject's blood pressure is to be monitored closely, [REDACTED] for 72 hours after administration of Ad-RTS-hIL-12. Assessment of vital signs is required prior to injection of Ad-RTS-hIL-12, and prior to veledimex dosing on day 1. The assessment of vital signs on day 3 and 7 should be performed prior to administration of veledimex.

Height and weight will be measured and recorded according to [Schedule of Study Procedures](#).

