## 10 SAFETY ASSESSMENTS

### 10.1 Adverse Events (AEs) and Definitions

*Adverse Event:* Any untoward medical occurrence in a patient or clinical investigation subject administered a pharmaceutical product that does not necessarily have a causal relationship to the treatment. An AE can therefore be any unfavorable and unintended sign including an abnormal laboratory finding, symptom, or disease temporarily associated with the use of a medicinal product, and any worsening of pre-existing conditions, regardless of causality to the medicinal product.

*Suspected Adverse Reaction:* Any AE for which there is evidence to suggest a causal relationship (reasonable possibility) between the drug and the AE. A suspected adverse reaction implies a lesser degree of certainty about causality than an adverse reaction.

*Adverse Reaction:* Any AE caused by the use of a drug. Adverse reactions are a subset of all suspected adverse reactions for which there is reason to conclude that the drug caused the event.

*Unexpected Adverse Reaction:* Any AE that is (a) not listed in the Investigator's Brochure, (b) not listed with the specificity and severity that is being observed, (c) not consistent with the risk information described in the general investigational plan or elsewhere in the current application (in the absence of an investigator brochure), and (d) listed as occurring with a class of drugs, but not specifically mentioned as occurring with the particular drug under investigation.

Adverse events may be treatment-emergent (i.e., occurring after initial receipt of investigational product) or nontreatment-emergent. A nontreatment-emergent AE is any new sign or symptom, disease, or other untoward medical event that begins after written informed consent has been obtained but before the subject has received investigational product.

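### No serum chemistry is scheduled in the seven veledimex dosing days, so the Section 6.7 hold-or-stop rule has no scheduled chemistry result to act on

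*Protocol*

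**What the plan says.** Veledimex is taken once daily on Days 1 to 7 (Section 6.2). Section 6.7 governs toxicity in that week: "Subjects who experience drug-related Grade 4 AEs during the first 7 days of oral dosing with veledimex will discontinue therapy". For drug-related Grade 3 events the investigator may interrupt or stop dosing. Section 10.1 defines an adverse event to include "any unfavorable and unintended sign including an abnormal laboratory finding", so a chemistry abnormality falls under the rule.

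In the Schedule of Study Procedures the "Serum Chemistry" row is marked at screening, Day 8, Week 6 and Week 12, and is blank at Days 1, 3 and 21. The visit lists in Sections 8.4.1 to 8.4.9 agree. Days 1 and 3 have hematology and research bloods, Day 1 also has urinalysis, and Days 4 to 7 have only dosing and the diary.

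Screening tests may be up to 28 days before the injection (Section 8.3). Section 8.1 accepts routine-care tests from before consent if they fall inside that window. Section 3.1 sets a maximum of 4 weeks between stopping chemotherapy and starting study treatment, but no minimum.

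Other safeguards are in place:
- Subjects "must be adequately hydrated with approximately 2000 ml of oral liquid" a day for the first 72 hours (Synopsis).
- Schedule footnote b adds: "Subjects must be instructed to maintain adequate oral hydration while taking veledimex".
- Section 8.3.1.3 says the subject's "blood pressure is to be monitored closely".
- Schedule footnote h describes the dipstick used on Day 1: "The urinalysis panel (dipstick) includes appearance, pH, specific gravity", among other items.
- Inclusion 6 requires earlier treatment toxicities to have settled to Grade 1 or lower.
- Section 10.9 calls for diagnostic tests once an event is recognised.

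**The concern.** A rule that holds or stops a drug within a seven-day course works only on information that arrives within the seven days. Symptoms, vital signs and Day 1 and Day 3 hematology do. A rise in transaminases, bilirubin or creatinine, or an electrolyte shift, without symptoms does not, unless someone orders an unscheduled test. By Day 8 there is no dose left to withhold. Stopping veledimex is also the product's own control on IL-12 expression (Section 5), so a timely result could be acted on.

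The second issue is attribution. Section 6.7 turns on whether an event is drug-related. A Day 8 abnormality would be judged against a value up to 28 days old, possibly taken during or soon after chemotherapy. Appendix 16.2 strongly recommends acetaminophen while warning people with liver disease against it, and Inclusion 11 admits hepatic metastases with ALT and AST up to 5 × ULN. Without a fresh pre-dose value it is hard to separate study product, earlier chemotherapy and acetaminophen.

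**Working it through.** The plan states no figure on this point, so the check is of the schedule against the dosing rule. The Schedule and Section 8.4 match, which rules out a table-reading error.

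**Inputs.** Doses on Days 1-7 (Section 6.2). Screening Day -28 to Day -1, with no Day 0 (Schedule). Chemistry at screening, Day 8, Week 6 and Week 12, which is 4 panels per subject. Up to 40 subjects (Section 4.3). The comparison adds a Day 1 pre-dose panel and a Day 3 panel.

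**Age of the pre-dose value at Day 1.** Day -1 gives 1 day; Day -28 gives 28 days. With a Day 1 pre-dose draw it is 0.

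**Gap from last pre-dose to first post-dose value.** Now: 1 + 7 = 8 days at best and 28 + 7 = 35 days at worst. With the addition: Day 1 to Day 3 = 2 days.

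**Doses a scheduled post-dose result can still inform.** Day 8: 0 of 7. Day 3: 5 of 7 (Days 3-7) if the result is back before that day's dose, otherwise 4 of 7 (Days 4-7).

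**Doses given after the onset day and before the first scheduled result**, for a silent abnormality starting on day d. Now this is 7 − d. With a Day 3 panel it is 3 − d for d ≤ 3, assuming onset before the draw and a result after that day's dose. For d ≥ 4 it is unchanged.

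| Onset day | Now | With Day 3 panel | Difference |
|---|---|---|---|
| 1 | 6 | 2 | 4 |
| 2 | 5 | 1 | 4 |
| 3 (before draw) | 4 | 0 | 4 |
| 4 | 3 | 3 | 0 |
| 5 | 2 | 2 | 0 |
| 6 | 1 | 1 | 0 |
| 7 | 0 | 0 | 0 |

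**Overlap of the screening window with chemotherapy.** The protocol gives no minimum interval, so the stop date is an assumption. If chemotherapy stopped s days before Day 1, then 28 − s days of the window precede the stop: s = 7, 14, 21, 28 gives 21, 14, 7, 0 days.

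**Panels.** Now 4 × 40 = 160. With the addition 6 × 40 = 240. Difference 80.

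**The case against.** The strongest reply is that nothing here is misstated. Table and visit lists agree, and Section 6.7 says what to do when an event occurs without promising chemistry surveillance. It can act on symptoms, vital signs, hematology and any unscheduled test. That stands, and it is why the point is an improvement rather than an error.

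The visible evidence also gives limited support for routine chemistry. The closest precedent, an intratumoral adenoviral IL-12 vector (Section 1.4.2), reported lymphopenia in 86%, fever in about 60% and nausea or vomiting in 24%, which scheduled hematology and symptom review cover. The chemistry events in Section 1.4.1 come from a different vector in 10 subjects: hypocalcemia in 2, raised creatinine in 1, raised amylase in 1 (not in this panel), and hyperglycemia in 30% attributed to parenteral nutrition. Much of the product background is blacked out, so product-specific safety data that would settle the need may exist unseen. These points stand as limits on the size of the benefit. They do not change the chemistry row, which is fully visible.

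The stale-baseline worst case is softened by Inclusions 5 and 6, which require chemotherapy interrupted and toxicities resolved. But neither requires a fresh panel before the first dose. Abnormalities persisting to Day 8 still fall inside the 21-day safety window and can reach the safety review committee, but too late for the dosing decision. Finally, the remedy misses onset on Days 4-7 and attaches no set consequence to an abnormal Day 1 value. Both are true.

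**Conclusion.** The concern holds as an optional, low-cost improvement. As written, no scheduled chemistry result can influence any of the seven doses, and the reference value for Day 8 is 1 to 28 days old. The listed safeguards reduce risk or respond to recognised events; none would reliably detect silent liver, renal or electrolyte toxicity.

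The gain is bounded. For onset on Days 1-3 before the draw, up to 4 fewer doses would be given before the abnormality is seen; for onset on Days 4-7 there is no gain. This assumes the Day 3 result is read the same day, after that day's dose, and that the abnormality is already detectable at the draw. How many subjects would benefit cannot be derived from the protocol. The point does not extend to the stopping boundaries or to the Section 6.4 rule for resuming held doses.

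**What to change.** Add the existing serum chemistry panel at two points:
- **Day 1**, drawn before veledimex and named as the baseline for grading laboratory changes. It is a reference value, not a new eligibility test.
- **Day 3**, with the result reviewed by the investigator the same day under Section 6.7.

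Update the Schedule of Study Procedures and Sections 8.4.2 and 8.4.4. Leave the dosing rules and the Day 8, Week 6 and Week 12 panels as they are.

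The cost is two more routine panels per subject (from 4 to 6), or up to 80 across 40 subjects. No visit is added: subjects already have blood drawn on both days, and footnote b already has them seen before dosing ("On Days 1 and 3 vital signs will be recorded prior to administration of veledimex"). The practical demands are to time the Day 1 draw before the first capsule and to have the Day 3 result read that day.

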#### **6.8 Severity Grading and Management of Local Reactions**

Injection of agents into tissue carries a potential risk of local reactions that may be characterized as intense immunologic reaction at or near the injection site. Local reactions will be graded according to the NCI CTCAE v.4.03 criteria.

As with all signs and symptoms, events should be recorded and graded as AEs according to NCI CTCAE v.4.03 criteria. Study stopping rules will not apply to a specific event if it is clearly unrelated to the Ad-RTS-hIL-12 injection.

